WBC	white blood cell

## 0. SYNOPSIS

## 0.1 Study title

MIRACLE (Methotrexate inadequate response patient with Rheumatoid Arthritis treated by Adalimumab in combination with Low-dose Methotrexate) Study

## 0.2 Schema

## 0.3 Objective

This study is intended to evaluate the optimal dosage of methotrexate (MTX) as an add-on therapy to adalimumab (ADA) in patients with rheumatoid arthritis (RA) who do not achieve remission by MTX monotherapy, and to measure erythrocyte MTX-polyglutamates (MTX-PG) concentration to evaluate its relation to the efficacy and safety of MTX therapy in RA patients.

## 0.4 Subjects

This study will be conducted in 300 patients with RA in Japan, South Korea, and Taiwan previously not treated with MTX, Janus kinase (JAK) inhibitor, or biological disease-modifying antirheumatic drugs (bDMARDs), and whose duration of disease is within 2 years from diagnosis.

RA patients (meeting the 1987 revised ACR criteria or 2010 ACR/EULAR criteria) aged  $\geq 18$  years ( $\geq 20$  years in Taiwan) whose disease activity at screening is SDAI >11.

## 0.5 Study treatment

Study treatment will start with MTX 6 to 8 mg/week, which will be promptly escalated to the maximum tolerable dose (MTD)  $\leq$ 25 mg/week (the maximum dose should be set according to the package insert of each country) in line with EULAR Recommendations 2016, and will be in principle maintained at the MTD from Week 12 onward. Also, the dosage of MTX will remain unchanged from Week 20 to 24 except for dose reduction/interruption due to an adverse drug reaction (ADR).

If the dosage of MTX is maintained  $\geq 10$  mg/week and remission (SDAI  $\leq 3.3$ ) is achieved at Week 24, the MTX therapy will be continued (ARM-1).

If SDAI remission is not achieved despite the dosage of MTX is maintained  $\geq 10$  mg/week at Week 24, a bDMARDs will be added to the treatment in line with EULAR Recommendations 2016. Subjects will subcutaneously receive ADA 40 mg as a bDMARD every other week up to Week 48, and be randomized to a group in which the MTD of MTX (10 to 25 mg/week) will be maintained (ARM-2) and a group in which the dosage of MTX will be reduced to 6 to 8 mg/week (ARM-3). Then, the efficacy and safety will be evaluated. If a subject becomes intolerable to MTX  $\geq 10$  mg/week at Week 24 due to an ADR or other relevant reasons, the subject will be terminated from the study at that time. The subject will

be also terminated from the study when subjects have received a non-ADA bDMARD or JAK inhibitor.

The primary endpoint will be the SDAI remission rate at Week 48 in the ADA/MTX-MTD Group (ARM-2) and ADA/MTX-Reduced Dose Group (ARM-3). Key secondary endpoints will be the SDAI remission rate at Week 24, the SDAI remission rate at Week 48 in MTX Monotherapy Group, the modified total sharp score (mTSS) at each assessment timepoint and changes from baseline to each assessment timepoint, and ACR20, ACR50, and ACR70 response rates at each assessment timepoint. Also, the correlation of the erythrocyte MTX-PG concentration to SDAI, mTSS, and ACR-N will be exploratorily evaluated.

## 0.6 Target number of subjects and study period

Target number of subjects	: 300 subjects
Enrollment period	: March 2018 to July 2020 (2 years
	and 5 months)
Intervention period	: 48 weeks
Data retrieval, analysis, and report generation periods	: 1 year
Total study period	: 4 years and 4 months

## 0.7 Contact

Inclusion/exclusion criteria, and others that require clinical judgment:

Lead Principal Investigator or Study Investigational Operator

EDC entry, etc.	: Data center
AE reporting	: SAE Report Center
Others	: Operation Center

## 1 Overview

## 1.1 Study Information

## 1.1.1 Study title

MIRACLE (Methotrexate inadequate response patient with Rheumatoid Arthritis treated by Adalimumab in combination with Low-dose Methotrexate) Study

## 1.1.2 Study identifying numbers

: D2E7-C000-401
: NCT03505008
: jRCT1031180088
: UMIN000030584

## 1.1.3 Version number and dates prepared and effective of the study protocol

Version number: 2.2

Date prepared:November 15, 2019Effective date:The amended protocol becomes effective on the day of entry in jRCT after
the approval by the Certified Review Board.

#### 1.2.5 Study Efficacy and Safety Advisor

The advisor comprises 2 physicians experienced in using ADA, designated by the Lead Principal Investigator, and selected from Department of Internal Medicine (1 from Division of Gastroenterology and 1 from Division of Rheumatology), Keio University School of Medicine. Principal investigator/sub-investigator may not be assigned as a member of the Study Efficacy and Safety Advisor.

Roles: Provides suggestions concerning the acceptability to continue the study and the necessity of protocol amendment upon request of the Lead Principal Investigator.

#### 1.2.6 Imaging Review Committee

The committee comprises physicians designated by the Lead Principal Investigator.

Roles: Reviews and evaluates the imaging data of hands and feet based on modified total sharp score (mTSS).

#### 1.2.7 Study Sites and Principal Investigators

See the Site List

Roles: Conducts this study at each study site in accordance with the protocol upon approval of the Certified Review Board/Ethical Review Board and Site Management (principal investigator).

## 2. Background information

## 2.1 Indication

## 2.1.1 Overview of indication

Rheumatoid arthritis (RA) is an autoimmune disease that causes chronic arthritis mutilans all over the body. The prevalence rate of RA is estimated to be about 1% worldwide (Firestein GS, 2017: 1115); 600,000 to 700,000 patients in Japan alone. The peak age of disease development in women is in their most productive years of 40's to 50's, resulting in not only physical disability, but also social restrictions, economic burden, and their family's mental strain. Main clinical manifestations include pain and swelling of joints in the hands and feet, as well as joint destruction and degeneration due to prolonged disease which not only generates chronic pain but also causes remarkable restriction on activities of daily living (ADL). About 70% of patients are said to develop bone erosion within 2 years if not appropriately treated (Howard A, et al. 1989: 585-91); thus, early therapeutic intervention is very important.

## 2.1.2 Comorbidities related to the indication

RA causes pain, joint fracture, and joint degeneration due to destructive polyarthritis that chronically occurs all over the body. Inflammation, if persists, causes not only pain but also irreversible destructions in the joints, resulting in remarkable reduction of ADL. RA is known to be accompanied by not only joint symptoms but also a high frequency of extracapsular symptoms such as scleritis, airway lesion, interstitial pneumonia, pleurisy, vasculitis, secondary Sjogren's syndrome, and secondary amyloidosis. Pulmonary lesions particularly affect vital prognosis, and often causes acute exacerbation. Furthermore, RA patients are known to have poorer vital prognosis compared to general population due to persistent inflammation and immunological abnormality which are risk factors of arteriosclerosis and malignant disease (Wolfe F, et al. 1994: 481-94). Also, immunosuppression associated with typical treatment is a high risk factor of infection-related complications.

## 2.1.3 Prognostic factors of the indication

Seropositive (rheumatoid factor and anti-CCP antibody), high disease activities, and bone erosion in early stage of disease are prognostic factors of future joint destruction, (Vastesaeger N, et al. 2009: 1114-21, Visser K, et al. 2010: 1333-7), and thus, are poor prognostic factors. Moreover, as mentioned above, the presence of interstitial pneumonia, vasculitis, and other extracapsular symptoms, and persistent inflammation are risk factors of arteriosclerosis and malignant disease. In addition, immunosuppression associated with typical treatment can cause serious infection, and thus can be a determining factor of prognosis.

## 2.1.4 Standard of care for the indication

DMARDs are clinically used to ease inflammation and pain, and prevent joint destruction in RA patients. EULAR Recommendations 2016 recommends to start using methotrexate (MTX) promptly upon diagnosis of RA, unless contraindicated, with a therapeutic goal to

achieve clinical remission in 6 months, and if unsuccessful, consider adding bDMARDs [tumor necrosis factor (TNF)- $\alpha$  inhibitor, abatacept, tocilizumab, and in some cases, rituximab] (Smolen JS, et al. 2017: 960-77). Low-dose steroid is used pertinent to an early therapeutic strategy up to 6 months, but the guideline recommends to reduce dose as promptly as clinically possible. Steroid pulse and high-dose steroid are also used sometimes for acute exacerbation of interstitial pneumonia and vasculitis.

Among bDMARDs, the efficacy of some TNF $\alpha$  inhibitors are known to increase when used in combination with MTX (Nam JL, et al. 2014: 516-28); however, an optimal dose of MTX in such combination use is unknown.

## 2.2 Study drug

## 2.2.1 Methotrexate (MTX)

MTX was approved in 1988 by the U.S. Food and Drug Administration as a drug for treatment of RA, and since then, has been widely used all around the world. MTX not only has a high response rate for treatment of arthritis, but also prevents the progression of joint destruction, and furthermore, its efficacy in improving QOL and vital prognosis have been demonstrated; thus, it became the first choice of standard treatment (Smolen JS, et al. 2017: 960-77).

It is also much inexpensive than bDMARDs. Because of such advantages, it is remains to a first-line drug recommended by EULAR Recommendations 2016 amid the presence of various bDMARDs today. A recommended maintenance dose of MTX is maximum tolerable dose of 25 to 30 mg/week (16 mg/week in Japan) when used in combination with folic acid. Also, TNF $\alpha$  inhibitor and other bDMARDs are now known to be more effective when used in combination with MTX than used alone.

Meanwhile, gastrointestinal symptoms, hepatic impairment, and myelopathy are known to be dose-dependent ADRs of MTX. In ADRs of MTX, gastrointestinal symptoms and hepatic enzymes increased are known to be alleviated by concomitant use of folic acid preparation (Tishler M, et al. 1988: 906-9, Morgan SL, et al. 1990; 33: 9-18.).

Also, while erythrocyte MTX-polyglutamates (PG) concentration has been reported to reflect the efficacy and safety of MTX (de Rotte MC, et al. 2015; 74:408-14), it has been pointed out that there is a possible difference in the MTX-PG concentration by  $\geq$ 1.4 fold between the Japanese and Western populations given the same dosage of MTX (Takahashi C, et al. 2017: e000363), suggesting a possibility of lower dose MTX to generate efficacy in the Japanese population when used in combination with ADA. Moreover, there has been no Asian country other than Japan in which study evaluating MTX-PG has been reported.

## 2.2.2 Adalimumab (ADA)

ADA was approved in the U.S. in 2002 as a drug for treatment of RA, and was launched in Japan in 2008 as the third anti-TNF- $\alpha$  inhibitor marketed in Japan. It has been marketed in South Korea and Taiwan since 2007. Its efficacy in preventing disease activities and progress of joint destruction has been confirmed in clinical studies (Breedveld FC, et al. 2006: 26-37).

## 2.3 Nonclinical and clinical studies

## 2.3.1 Nonclinical studies

MTX inhibited hind paw inflammation, managed body weight gain, and inhibited joint destruction in mice with collagen-induced arthritis at repeated doses of 0.05 and 0.1 mg/kg/day or 0.6 to 1.2 mg/kg/week divided into 3 doses per week. MTX also inhibited hind paw inflammation and joint destruction in the chronic phase in mice with group A streptococcal cell wall-induced arthritis, an adjuvant arthritis model, at repeated doses of 0.125 mg/kg/day. MTX inhibited inflammation of the untreated paw in mice with adjuvant arthritis at intermittent oral doses of 0.15 to 0.6 mg/kg/week or 0.375 mg/kg/3 weeks. ADA (0.01, 0.1, 0.5, 1, and 10 mg/kg) prevented arthritis in transgenic mice bearing the human TNF $\alpha$  gene in a dose-dependent manner when administered intraperitoneally three times weekly from 1 to 8 weeks of age. The ED50s were 0.25 mg/kg (joint score) and 0.48 mg/kg (histopathological score).

## 2.3.2 Clinical studies

Like other TNF $\alpha$  inhibitors, the efficacy of ADA used in combination with MTX has been confirmed (Breedveld FC, et al. 2006: 26-37).

Regarding dosage of MTX in combination with ADA, in a study conducted in Western MTX naïve patients which the combination of MTX with ADA was simultaneously started, the results showed no change in efficacy with dosage of MTX  $\geq$ 10 mg/week (Burmester GR, et al. 2015:1037-44). Meanwhile, another study has been conducted in the U.S. to determine whether dosage of MTX may be reduced when ADA is added in MTX failure patients (Kaeley GS, et al. 2016: 1480-9), but no conclusion has been drawn.

Also, there was a study (HOPEFUL 1) conducted in Japanese subjects to evaluate the efficacy of ADA in combination with MTX (Takeuchi T, et al. 2014: 536-43); however, this study was conducted back then when the MTX dose was restricted to 8 mg/week or lower in Japan. A stratified analysis on the results of post-marketing surveillance demonstrated that the efficacy hits plateau at an MTX dose of  $\geq$ 6 mg/week as a concomitant use in bDMARDs naïve patients. Meanwhile, in terms of safety, infection and other risks increase at an MTX dose of  $\geq$ 10 mg/week. Accordingly, MTX 8 mg/week is proposed for concomitant therapy in bDMARDs naïve patients. Yet, the results were based on a retrospective observational study, and further researches are required.

## 2.4 Risks and benefits to subjects

## 2.4.1 Expected benefits

MTX is a drug for which the efficacy for RA as a first-line medication has been adequately proven, and is expected to effectively control RA in this study. Also, concomitant use of a bDMARD after 24 weeks of treatment with MTX is in compliance with EULAR Recommendations 2016.

Furthermore, if low-dose MTX provides adequate therapeutic effect when used in combination with ADA, it would reduce MTX-related ADRs that dose-dependently increase, which may not be of a direct benefit for subjects taking in this study, but could help

establishing more optimal drug usage, and eventually generate benefits for RA patients in the future.

## 2.4.2 Anticipated risks and disadvantage

Possible risks in subjects include ADRs related to MTX and ADA. MTX-related ADRs include bone marrow depression, as well as infections such as interstitial pneumonia and pneumocystis pneumonia, gastrointestinal disorder and liver disorder, and also lymphoproliferative diseases. ADRs related to ADA include lupus-like syndrome and demyelinating disease (multiple sclerosis, etc.) in addition to those mentioned above. The usages of drugs in this study are in line with EULAR Recommendations 2016, and the benefits, that is, control of disease activities, and the risk of ADRs were considered when the guideline was prepared, and this study is also in line with the guideline.

Investigational blood sampling may become disadvantage, but the amount of which is not much more than what would be required for usual clinical practice, and thus, the risk thereof should be negligible.

There is a potential risk of invasion of privacy since this study involves clinical samples and medical information, but such risk will be minimized through anonymization.

# 2.5 Route of administration, dosage and administration, and duration of treatment

#### <MTX>

MTX should be started at a dosage of 6 to 8 mg/week, and promptly escalated to the maximum tolerable dose (MTD)  $\leq$ 25 mg/week (the maximum dose should be set according to the package insert of each country), and in principle maintained at the MTD from Week 12 onward. Also, the dosage of MTX should remain unchanged from Week 20 to 24 except for dose reduction/interruption due to an ADR. The drug will be taken orally. In principle, a weekly dosage should be taken once or twice in a day. The package insert of each country should be referred to for the details of dosage regimen. The duration of treatment will be 48 weeks.

The route of administration, and dosage and administration were selected within the range specified in the package insert of each country by referring to the EULAR Recommendations 2016. The duration of treatment was defined as the duration required for the efficacy assessments in reference to the EULAR Recommendations 2016.

#### <ADA>

If a subject maintains MTX  $\geq 10$  mg/week and SDAI remission is not achieved at Week 24, the subject should start receiving ADA 40 mg subcutaneously every other week up to Week 48 (thus, the duration of treatment will be 24 weeks). The package insert of each country should be referred to for the details of dosage regimen.

The route of administration, and dosage and administration were selected according to the package insert. The duration of treatment was defined as the duration required for the efficacy assessments in reference to the EULAR Recommendations 2016.

## 2.6 Applicable rules, etc.

All investigators involved in this study must comply with "World Medical Association, Declaration of Helsinki (Revised version dated October 2013)," "ICH-GCP," and this protocol when conducting this study. In Japan, "Clinical Trials Act" must also be complied.

## 2.7 Study population

The study population will be patients with RA in Japan, South Korea, and Taiwan previously not treated with MTX, JAK inhibitor, or bDMARDs, and whose duration of disease is within 2 years from diagnosis. Subjects will be stratified by countries (Japan, South Korea, and Taiwan) as a stratification factor.

## 2.8 Reference and data

See Chapter 16.2.

## 3 Objective

## 3.1 Background

The efficacy of ADA for treatment of RA patients is known to increase when used in combination with MTX. However, an optimal dose of MTX in such combination use is not fully studied, and thus, the dosage of MTX monotherapy is often continued to use clinically.

## 3.2 Objective

This study is intended to evaluate the optimal dosage of MTX as an add-on therapy to ADA in patients with rheumatoid arthritis (RA) who did not achieve remission by MTX monotherapy, and to measure erythrocyte MTX-polyglutamates (PG) concentration to evaluate its relation to the efficacy and safety of MTX therapy in RA patients.

## 3.3 Purpose

A lower dosage of MTX, which is effective in combination with ADA in MTX-refractory RA patients is expected to reduce MTX-related ADRs that dose-dependently increase.

## 4 Study design

## 4.1 Endpoints

## 4.1.1 Primary endpoint

• SDAI remission rate at Week 48 in Concomitant ADA MTX Maximum Tolerable Dose Extended Treatment Group and Concomitant ADA MTX Dose Reduction Group

## 4.1.2 Secondary endpoints

- SDAI remission rate at Week 24
- SDAI remission rate at Week 48 in MTX Monotherapy Group

- ACR20, ACR50, and ACR70 response rate at each assessment timepoint
- HAQ remission rate at each assessment timepoint
- SDAI, CDAI, DAS28-ESR, and DAS28-CRP at each assessment timepoint, and change from baseline to each assessment timepoint
- Tender joint count, swollen joint count, VAS (physician- and patient-reported), HAQ, CRP, ESR, MMP-3, RF, and anti-CCP antibody at each assessment timepoint, and change from baseline to each assessment timepoint
- Modified total sharp score (mTSS) at each assessment timepoint, and change from baseline to each assessment timepoint
- Structural remission (mTSS  $\leq 0.5$ ) rate at each assessment timepoint
- Vital signs and laboratory findings at each assessment timepoint, and change from baseline to each assessment timepoint
- Status of AE (Up to Week 24, and up to Week 48 for each ARM)

#### 4.1.3 Exploratory endpoints

- Erythrocyte MTX-PG concentration at Weeks 0, 4, 8, 12, 24, 36, and 48
- Blood cytokine (IL-6, VEGF) at Weeks 0, 24, and 48
- Plasma micro RNA at Week 24
- Serum anti-adalimumab antibody at Weeks 24 and 48

#### [Rationale]

RA may be clinically evaluated from 3 aspects; the activity, function, and structure of arthritis. The standard indices of RA assessments internationally recognized are SDAI and ACR20/50/70 for disease activity assessment, HAQ for functional assessment, and TSS for structural assessment.

## 4.2 Study method

This is a multicenter, open-label, randomized, interventional study conducted in patients with RA in Japan, South Korea, and Taiwan.

Principal investigator/sub-investigator shall confirm the inclusion/exclusion criteria of each patient, and upon his/her consent, enter necessary information in IWRS. If there is no issue with the information entered in IWRS, the subject will be given a subject ID. The enrollment completes when the subject ID for a patient is entered into the EDC system.

After obtaining the consent, a subject will start receiving MTX, and if the subject achieves the SDAI remission at Week 24, will continue to receive MTX until Week 48. If the subject does not achieve the SDAI remission, ADA 40 mg should be started as an add-on therapy up to Week 48, and the subject will be randomized to either a group in which the dosage of MTX is maintained or a group in which the dosage of MTX is reduced.

## 4.3 Bias

#### 4.3.1 Randomization

If a subject does not achieve to clinical remission (SDAI  $\leq$ 3.3) at Week 24 despite the maintenance of MTX dose at  $\geq$ 10 mg/week, the subject will start receiving ADA as an add-on therapy. Subjects then will be stratified by countries (Japan, South Korea, and Taiwan) as a stratification factor, and for each stratum, subjects will be randomized at a 1:1 ratio to either a group in which the MTD of MTX (10 to 25 mg/week) will be maintained (ARM-2), and a group in which the dosage of MTX will be reduced to 6 to 8 mg/week (ARM-3). Upon completion of Week 24 assessments, principal investigator/sub-investigator shall enter the Week 24 dosage of MTX, tender joint count (28 joints), swollen joint count (28 joints), VAS (physician- and patient-reported; 10 cm scale), and CRP in IWRS. If all necessary information is entered, a relevant treatment group in line with the status of randomization (ARM-1, ARM-2 or ARM-3) will be issued by IWRS.

The MTX dosage shall be either 6 mg/week or 7.5 mg/week in subjects in ARM-3 whose maintenance dose of MTX at Week 24 is 10 mg/week.

#### 4.3.2 Blinding

No blinding will be performed in this study.

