## 4.8 Storage of randomization code, and unblinding process

Randomization code for this study will be retained in the IWRS system. This is not a blinded study, and therefore, no unblinding process will be specified.

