#### 7.2 Efficacy assessments

#### 7.2.1 X rays of hands and feet

In accordance with the assessment schedule presented in the following table, X rays of subjects' hands and feet will be performed at screening, and Weeks 24 and 48 (or at early termination). The X-rays of the hands and feet are unnecessary to be performed for early termination if early termination occurs within 28 days after the last X-rays. The X-ray image of the hands and feet should be sent to the study secretariat along with the subject ID. The X-ray image of the hands and feet will be independently reviewed by the X-ray Imaging Review Committee to evaluate bone erosions in the regions specified on the left side of the figure shown below, and also to evaluate joint space narrowing in the results will be sent to the data center.

Bone erosions will be evaluated for each region in accordance with the following score:

Score 1: Small bone erosion

Score 2: Large bone erosion (Not extend over the imaginary middle of the bone)

Score 3: Large bone erosion (Extends over the imaginary middle of the bone)

Score 5: Complete collapse of the joint

The score will be 0 to 5 for each hand region, and 0 to 10 for each foot region. The maximum total erosion score of both hands will be 160 points, and that of both feet will be 120 points.

Joint space narrowing will be evaluated for each region in accordance with the following score:

Score 1: Localized or merely suspected

Score 2: Generalized narrowing (≥50% joint space remaining)

Score 3: Generalized narrowing (≤50% joint space remaining) or subluxation

Score 4: Disappearance of joint space, or anchylosis or luxation

The maximum total joint space narrowing score of both hands will be 120 points, and that of both feet will be 48 points.

Source: Swinkels HL, et al. 2001: 176-90

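### The plan lets Week 48 and early-termination films be scored by a reader who knows the treatment arm; image reading should be masked to arm

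*Protocol*

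**What the plan says.** - Protocol 4.3.2, under the heading on bias, consists of one sentence on blinding: "No blinding will be performed in this study". Section 4.8 adds "This is not a blinded study, and therefore, no unblinding process will be specified". Neither makes an exception for outcome readers.
- Protocol 1.2.6 sets up the Imaging Review Committee: "The committee comprises physicians designated by the Lead Principal Investigator". It states no exclusion.
- Protocol 1.2.5, immediately before it, does state one for another body: "Principal investigator/sub-investigator may not be assigned as a member of the Study Efficacy and Safety Advisor".
- Protocol 7.2.1 describes the film flow: "The X-ray image of the hands and feet should be sent to the study secretariat along with the subject ID". The images "will be independently reviewed by the X-ray Imaging Review Committee to evaluate bone erosions", and results go to the data center. The section does not define what the review is independent of, and gives no number of readers or rule for disagreements.
- Films are taken at screening, Week 24 and Week 48 or early termination (Protocol 7.2.1). The arm is issued after the Week 24 assessments (Protocol 4.3.1).
- mTSS is a secondary endpoint: "Modified total sharp score (mTSS) at each assessment timepoint, and change from baseline to each assessment timepoint" (Protocol 4.1.2). The synopsis lists it among the key secondary endpoints. ARM-2 and ARM-3 are compared on mTSS change and on structural remission at Week 48 (Protocol 9.2.1.2; SAP 6.2.8 and 6.2.9).

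**The concern.** Open treatment is unavoidable in a comparison of maintained against reduced methotrexate as it is designed here. Open image reading is not, because films are stored, sent to one secretariat and scored by a committee away from the clinic.

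A reader who knows that methotrexate was reduced may, without intending to, look harder for new damage, or discount it. The scale leaves room for this: in 7.2.1 the lowest joint space narrowing score, 1 point, covers a finding that is only suspected. Any such tendency would act on one arm and not the other, so it would bias the comparison and not merely add noise.

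At stake is the trial's structural evidence. The rationale in Protocol 4.1 names activity, function and structure as the three aspects by which RA is assessed, and gives the Sharp score as the structural measure. Joint counts and both global VAS scores already come from people who know the arm, so there is good reason to protect an outcome that can be protected easily.

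**Working it through.** The point rests on no planned figure, so the check is to set the relevant sections side by side.

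| Question | Where | What is found |
|---|---|---|
| Is any reader masked to arm? | Protocol 4.3.2, 4.8 | No blinding; no exception |
| May an investigator be a reader? | Protocol 1.2.6 | Not excluded; compare the bar in 1.2.5 |
| How are films labelled? | Protocol 7.2.1 | By subject ID |
| Who can link that ID to an arm? | Protocol 4.2, 4.3.1, 6.1 | The ID is issued through IWRS and entered in EDC; IWRS issues the arm; EDC records it |
| Does any other step mask the reading? | SAP 2.3 | Arm is removed for the data handling meeting only |

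**Step 1: can a reader know the arm?** Yes, if the reader is an investigator who treats the subject, or has IWRS or EDC access. Nothing in 1.2.6 or 7.2.1 rules out either.

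**Step 2: which films are exposed?** The arm does not exist until after the Week 24 assessments. Screening and Week 24 films record the joints before randomized treatment, so the exposure is chiefly the Week 48 film, or an early-termination film taken after Week 24.

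**Step 3: which analyses use those films?** The ARM-2 versus ARM-3 comparisons of mTSS change to Week 48 (from baseline and from Week 24) and of structural remission at Week 48. SDAI (Protocol 7.2.4) is built from joint counts, two VAS scores and CRP, so the primary non-inferiority test contains no film score. The mTSS covariate in the logistic model for Week 48 remission (SAP 6.1) covers screening to Week 24 only.

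**Step 4: how sensitive is structural remission to one call?** The cut-off is mTSS of 0.5 or less; the smallest call is 1 point.
- Subject otherwise at 0, single or consensus score: 0 + 1 = 1, above 0.5. The classification changes.
- Same subject, two readers averaged, only one making the call: (0 + 1)/2 = 0.5, not above 0.5. No change.
- Subject already above 0.5: no change in either case.

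The result depends on the number of readers and on how many subjects lie at or below the cut-off. The documents give neither, so no percentage shift can be derived.

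**The case against.** The strongest reply is that 4.3.2 only describes open treatment. It follows the randomization section, agrees with the open-label description in 4.2, and the only consequence drawn in 4.8 is that no unblinding procedure is needed. The SAP does not read it as a ban on all masking, since arm is removed before the data handling meeting. Films also leave the site, go to a separate committee for independent review, and carry a coded ID without the subject's name (Protocol 12.3).

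Much of this stands. A reader might infer that treating investigators will score their own subjects' films, or that readers will know the arm. The documents do not say so, and the missing bar in 1.2.6 does not prove it. The subject ID alone does not reveal the arm.

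What does not stand is the step from these safeguards to masking. *Independently* could mean independent of the sites or of a second reader, and neither hides the arm. A coded ID hides identity, not allocation, from anyone with study access.

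A reader might also want film order masked. Knowing order without arm affects ARM-2 and ARM-3 alike and does not by itself bias their comparison, so that is a separate choice about reading method.

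One caution: in the copy read, a sentence in 7.2.1 breaks off between joint space narrowing and the sending of results. The lost words probably concern joint regions, but the section should be checked in full.

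**Conclusion.** The point holds as a gap that the plan leaves open: followed as written, it permits arm-aware scoring of the Week 48 or early-termination films. This could bias the between-arm results for mTSS change and structural remission. It does not touch the primary SDAI comparison, the sample size or the error rate.

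No size can be put on the bias. A shift of several percentage points in structural remission might be inferred from the 1-point minimum score and the 0.5 cut-off. That would require a single or consensus reader, a subject otherwise at or below the cut-off, and an assumed frequency of biased calls that the documents do not supply.

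Nor should mTSS be called the only outcome that can be protected: laboratory measures such as CRP and ESR are also less open to assessor bias.

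The conclusion assumes that no masking rule exists outside the protocol and SAP, for example in a reading manual. If one does, the remedy is to say so in the protocol. The change is worth making because it protects key secondary endpoints at little effort; it is not a condition for the validity of the primary result.

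**What to change.** 1. **Protocol 4.3.2:** state that treatment is open but image reading is masked to treatment arm.
2. **Protocol 1.2.6:** state that a reader may not score films of subjects he or she treats.
3. **Protocol 7.2.1:** have the secretariat replace the subject ID with a reading code and remove site identifiers before films go to the committee. While this section is open, also state the number of readers and how disagreements are settled, because the structural-remission result depends on both.

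If films have already been read, report the conditions of reading, or re-read them masked to arm.

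The cost is protocol wording and a small amount of re-coding by the secretariat, which already receives every film; the documents give no figure for this work. Committee, films, visits, treatment, sample size and analyses stay the same. Films need not be held until the last one arrives, so the planned summaries of pre-randomization data (Protocol 9.7) are not delayed.
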